7.2 Methods and Timing for Assessing, Recording, and Analyzing Safety Parameters

CGMI-V is a low risk behavioral intervention designed to support ADRD caregivers emotionally within the first two years of placement of a family member with ADRD in a long-term care facility. The proposed intervention poses minimal risk to participants.

Identified safety parameters identified above in 7.1 will be assessed at: pre-enrollment screening, and the three data collection points (baseline and 8 and 24-weeks).

Interventionists will implement suicide protocol in the event of reported suicidal ideation during group sessions.

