6.2.3 Completion/Final Evaluation (24 weeks from baseline)

This study will not use a final visit. All Completion/Final evaluations will be performed using computer-assisted telephone interviewing (CATI). The following study outcomes will be measured at 24 weeks from baseline for maintenance effects:

- Caregiver grief
- Caregiver depressive symptoms
- Caregiver anxiety symptoms
- Caregiver positive states of mind
- Caregiver conflict with facility staff
- Caregiver satisfaction with care in the facility
- Caregiver knowledge of ADRD
- Caregiver sense of loss
- Caregiver guilt
- Caregiver role captivity
- Caregiver adherence to CGMI-V /Satisfaction Survey (intervention condition)
- Changes in caregiver and care recipient status

Based on our previous pilot studies²⁵⁻²⁷, we do not anticipate early termination of the CGMI-V study. We will document reasons for participant voluntary drop-out and will ask participants who may have dropped out prior to completing the 8 group-based CGMI-V sessions to participate in the 8 and 24-week follow-up assessments.

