7 SAFETY ASSESSMENTS

Participant safety will be monitored once each individual is screened and enrolled in the study. CGMI-V is a low risk behavioral intervention designed to support ADRD

caregivers emotionally in the context of placement of a family member with ADRD in a long-term care facility. The proposed intervention poses minimal risk to participants.

During screening and data collection for both conditions, there is potential risk for caregivers to disclose:

- Depressive symptoms (high levels indicative of clinical depression)
- Suicidal ideation

During the Chronic Grief Management Intervention-Video (CGMI-V) intervention implementation, emotional upset may occur especially during the last four sessions, when grief processing becomes the focus of the intervention. Caregivers may disclose high levels of:

- Depressive symptoms (high levels indicative of clinical depression)
- Suicidal ideation

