7.1 Specification of Safety Parameters

- A score greater than 16 points (indicative of risk for clinical depression) on the Center for Epidemiological Studies-Depression Scale (CES-D)⁴⁰
- A score >1 on the PHQ 9 suicidal assessment item: “Thoughts that you would be better off dead or of hurting yourself”
- Verbalizing suicidal ideation during CGMI-V group session intervention implementation

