7.3 Adverse Events and Serious Adverse Events

An **adverse event (AE)** is generally defined as any unfavorable and unintended diagnosis, symptom, sign (including an abnormal laboratory finding), syndrome or disease which either occurs during the study, having been absent at baseline, or if present at baseline, appears to worsen. An example of an Adverse Event (AE) anticipated for this study would be, during data collection, a Center for Epidemiological Studies-Depression Scale (CES-D) score greater than 16 points, indicative of risk for clinical depression. Whether or not this high

score is associated with study participation, we will monitor and report it as an AE, per protocol.

A **serious adverse event (SAE)** is generally defined as any untoward medical occurrence that results in death, is life threatening, requires inpatient hospitalization or prolongation of existing hospitalization, results in persistent or significant disability/incapacity, or is a congenital anomaly. An example of a Serious Adverse Event (SAE) anticipated for this study would be a participant's endorsement of suicidal ideation when screened with the PHQ-9 or disclosing suicidal ideation in a group session. Whether or not associated with study participation, we will monitor and report suicidal ideation or intention as a SAE, per protocol adopted from the Office of the Human Research Protection Program's *Research Protocols and Risk of Suicide Guidelines* (2012).

An Unanticipated Problem (UP) for this study would be any study participant incident, experience or outcomes that are unexpected in severity or frequency suggesting that participants are at greater risk of harm than anticipated. An example of an Unanticipated Problem (UP) for this study would be a participant becoming extremely upset with intervention content, to the point of dropping off from the study as a consequence. Whether or not associated with study participation, we will monitor and report per protocol.

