7.4 Reporting Procedures

The PI will use standardized NIA forms to report all adverse effects (AEs) and serious adverse effects (SAEs) (except death) in writing to the NIA Program Officer (PO), Safety Officer (SO) and Rush University IRB on a **quarterly** basis.

Any Unanticipated SAEs not listed in the Data Safety Monitoring Plan related to the intervention will be reported by the PI on an expedited basis within **48 hours** from determination of occurrence to the NIA PO, SO, and IRB, following-up with a written corrective plan with measures to prevent reoccurrence.

The PI will report any participant death whether or not related to study participation and regardless of intervention condition to NIA PO, SO, and IRB on an expedited basis within **24 hours** from determination of occurrence.

Unanticipated problems including other incidents, outcomes, or experiences that are not SAEs (e.g. data breach, confidentiality threat) will be reported by the PI using standardized forms to NIA PO, SO, and IRB within **48 hours**, including a corrective plan and measures to prevent reoccurrence. .

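### No method is described for eliciting the adverse events of section 7.3 beyond depression score and suicidality; with 10 planned post-baseline contacts in CGMI-V and 2 in MT, event counts may be inflated in CGMI-V

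*Combined protocol and SAP*

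**What the plan says.** Section 7.1 names three safety parameters: a CES-D score above 16, "A score >1 on the PHQ 9 suicidal assessment item", and "Verbalizing suicidal ideation during CGMI-V group session intervention implementation". Section 7.2, which is headed as the methods and timing section, covers only these: "Identified safety parameters identified above in 7.1 will be assessed at: pre-enrollment screening, and the three data collection points".

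Section 7.3 is wider. An adverse event is any unfavourable and unintended diagnosis, symptom, sign, syndrome or disease that is new or worse than at baseline. A serious one includes an event that "requires inpatient hospitalization or prolongation of existing hospitalization, results in persistent or significant disability/incapacity". Suicidal ideation disclosed in a group session is given as an example of an SAE.

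The schedule in 6.1 has no row for adverse events. The nearest item is a change-in-status survey at weeks 8 and 24, listed in 6.2.2 and 6.2.3 as "Changes in caregiver and care recipient status". It is not restricted to one arm, but its questions are not described. Section 10.3.4 promises ongoing assessment of potential adverse effects without giving a method.

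On reporting, 7.4 sends all AEs and SAEs other than deaths in quarterly, deaths within 24 hours regardless of cause or arm, and non-SAE unanticipated problems within 48 hours. A further 48-hour route is worded "Any Unanticipated SAEs not listed in the Data Safety Monitoring Plan related to the intervention will be reported by the PI".

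**The concern.** An event that no one is scheduled to ask about tends to be recorded when a participant happens to mention it, and the opportunity to mention it differs by arm. CGMI-V caregivers meet an interventionist weekly for eight weeks; MT caregivers receive written material at baseline and have no planned contact before week 8. In addition, one of the three parameters in 7.1, which is also an SAE example in 7.3, can arise only in a CGMI-V session.

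If true rates were equal, recorded counts could therefore look worse in CGMI-V, and events in MT could go unrecorded. The Safety Officer, who reviews adverse events twice a year under 7.6, would be seeing the two arms with different sensitivity. Yet section 7 recognises a safety issue in both arms: "During screening and data collection for both conditions, there is potential risk for caregivers to disclose" high depressive symptoms or suicidal ideation.

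**Working it through.** The documents give no event rate, contact count or detection figure, so there is none to reproduce. The contact count below comes from the schedule; everything after it is an illustration under stated assumptions.

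**Planned contacts after baseline** (Précis, 5.1, 6.1)
- CGMI-V: 8 sessions + 2 interviews = 10.
- MT: 0 + 2 = 2.
- All 8 extra contacts fall in weeks 1 to 8. Between week 8 and week 24 each arm has one planned contact, the week-24 interview.

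**Model.** Let p be the assumed chance that an event is mentioned at any one later contact, and k the number of contacts still to come. Then P(recorded) = d(k) = 1 − (1 − p)^k. Full attendance is assumed, and p is taken to be the same in a session and in an interview.

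**Event before session 1** (all contacts still to come): d(10) against d(2).
- p = .10: .651 against .190, ratio 3.4.
- p = .30: .972 against .510, ratio 1.9.

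**Events spread evenly over 24 weeks.** In CGMI-V an event in week w (1 to 8) is followed by sessions w to 8 and two interviews, so k = 11 − w, running from 10 down to 3. In MT an event in those weeks has k = 2. In weeks 9 to 24, k = 1 in both arms.
- CGMI-V: [d(3) + d(4) + … + d(10) + 16·d(1)] / 24
- MT: [8·d(2) + 16·d(1)] / 24

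For p = .10 the CGMI-V sum d(3) to d(10) is 3.848, so (3.848 + 1.6)/24 = .227; MT is (1.52 + 1.6)/24 = .130; ratio 1.75. For p = .30 the sum is 6.923, so (6.923 + 4.8)/24 = .488; MT is (4.08 + 4.8)/24 = .370; ratio 1.32.

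| Assumed p | CGMI-V | MT | Ratio, 24 weeks | Ratio, events in weeks 1–8 |
|---|---|---|---|---|
| .05 | .126 | .066 | 1.92 | 2.86 |
| .10 | .227 | .130 | 1.75 | 2.53 |
| .20 | .378 | .253 | 1.49 | 2.04 |
| .30 | .488 | .370 | 1.32 | 1.70 |
| .50 | .656 | .583 | 1.13 | 1.29 |
| .80 | .866 | .853 | 1.02 | 1.04 |
| 1.0 | 1.000 | 1.000 | 1.00 | 1.00 |

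**In counts.** With an assumed true rate of 10% per arm (7.2 of 72) and p = .20, expected recorded events are 7.2 × .378 = 2.7 in CGMI-V and 7.2 × .253 = 1.8 in MT. If every event is elicited at each interview (p = 1), the ratio is 1.00.

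**The case against.** Several stronger readings are tempting, and the documents do not support them.

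- **That other events surface only if volunteered.** The change-in-status survey covers the caregiver in both arms. What it asks is not stated, and neither the Research Assistant manual nor the Data Safety Monitoring Plan is available here. What can be said is that no elicitation is described, not that none will take place.
- **That a 5:1 contact ratio means a 5:1, or even a 1.9 to 3.4, detection ratio.** The excess ends at week 8, and 1.9 to 3.4 applies only to events before session 1. Missed sessions, or more reticence in a group than in a one-to-one call, would shrink the ratio further.
- **That expedited reporting is confined to intervention-related events.** Deaths go in within 24 hours whatever the cause or arm, and non-SAE unanticipated problems within 48 hours with no relatedness limit. Only the unanticipated-SAE route carries that limit, and all non-fatal SAEs are still reported quarterly. The clause affects when an event is reported, not whether it is counted, so it is no source of arm bias.
- **That section 7 says interviews provoke SAEs.** It speaks of caregivers disclosing symptoms or ideation, which 7.3 already treats as reportable regardless of association.

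It is also fair to say that no between-arm safety test is planned in 9.5, and that the most plausible harms are psychological: grief, depression and anxiety are measured identically in both arms at weeks 8 and 24, by blinded interviewers. This limits what is at stake. It does not supply a method for the wider events that 7.3 says will be collected, and it does not remove the one parameter that only CGMI-V can generate.

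**Conclusion.** The concern stands as a gap in ascertainment. Section 7.3 defines events for which neither 7.2 nor the schedule describes any elicitation, and planned post-baseline contact is 10 against 2. Event counts may be inflated in CGMI-V relative to MT. To state that they are biased would go further than the documents allow, because the content of the status survey is unknown.

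The size is illustrative: about 1.3 to 1.75 over 24 weeks for an assumed p of .30 to .10, equal true rates, evenly spread events and full attendance. It approaches 1 if caregivers nearly always report. With 72 per arm and few SAEs expected, even the lower figure could colour a reading of the counts. The asymmetry that is directly written into the plan is ideation voiced in sessions.

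A separate question of timing remains in 7.4. An unexpected, non-fatal SAE in MT, or one linked to a study interview, does not clearly fit the route limited to the intervention. The unanticipated-problem route can be read as excluding SAEs or merely as including non-SAEs, while 7.3 says unanticipated problems are reported whether or not associated with participation. These sections need to be reconciled.

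**What to change.** 1. Add one identical closed question set, built on the SAE criteria in 7.3 and asked with reference to the period since the last interview, to the existing change-in-status survey at weeks 8 and 24 in both arms. Give it a row in 6.1 and refer to it in 7.2. The interviewers are blinded under 10.1, so ascertainment would be on the same footing in both arms.
2. In any tabulation of safety by arm, use the interview-solicited events, and list events first disclosed in sessions separately.
3. Reconcile 7.4 with 7.3, so that it is clear by which route and when a non-fatal unexpected SAE in MT, or one linked to a study interview, is reported. Carry the result into section 12, item 5.

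The cost is protocol wording and a few questions in calls already planned: slightly longer interviews and possibly a few more reports. No visit, staff post or design element changes.

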7.3 Adverse Events and Serious Adverse Events

An **adverse event (AE)** is generally defined as any unfavorable and unintended diagnosis, symptom, sign (including an abnormal laboratory finding), syndrome or disease which either occurs during the study, having been absent at baseline, or if present at baseline, appears to worsen. An example of an Adverse Event (AE) anticipated for this study would be, during data collection, a Center for Epidemiological Studies-Depression Scale (CES-D) score greater than 16 points, indicative of risk for clinical depression. Whether or not this high

score is associated with study participation, we will monitor and report it as an AE, per protocol.

A **serious adverse event (SAE)** is generally defined as any untoward medical occurrence that results in death, is life threatening, requires inpatient hospitalization or prolongation of existing hospitalization, results in persistent or significant disability/incapacity, or is a congenital anomaly. An example of a Serious Adverse Event (SAE) anticipated for this study would be a participant's endorsement of suicidal ideation when screened with the PHQ-9 or disclosing suicidal ideation in a group session. Whether or not associated with study participation, we will monitor and report suicidal ideation or intention as a SAE, per protocol adopted from the Office of the Human Research Protection Program's *Research Protocols and Risk of Suicide Guidelines* (2012).

An Unanticipated Problem (UP) for this study would be any study participant incident, experience or outcomes that are unexpected in severity or frequency suggesting that participants are at greater risk of harm than anticipated. An example of an Unanticipated Problem (UP) for this study would be a participant becoming extremely upset with intervention content, to the point of dropping off from the study as a consequence. Whether or not associated with study participation, we will monitor and report per protocol.

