Control condition. Caregivers in the control condition will receive Minimal Treatment (MT) consisting of written information about late-stage ADRD (Alzheimer's Association) at baseline. The Project Director will mail caregivers in the MT control condition all written information materials.

4 **SELECTION AND ENROLLMENT OF PARTICIPANTS**

We will recruit a sample of 144 ADRD caregivers who have a family member residing in dementia care or memory care units in long-term care facilities located in the Chicago metropolitan area. We have well-established collaborating relationships with 35 long-term care facilities that will give us access to a diverse pool of approximately 1,000 ADRD family caregivers.

4.1 **Inclusion Criteria**

Participants must meet all inclusion criteria listed below in order to participate in this study.

- 21 years of age or older
- Identified as family member, fictive kin (self-identified family member) or partner of care recipient at any time post permanent placement of care in LTCF
- Care recipient has a documented ADRD diagnosis and resides in any type of unit in a long-term care facility
- Possessing self-reported basic computer literacy and in-home internet access
- Able to speak, read, and write English
- Not currently attending another ADRD caregiver grief management group

- Experiencing high to moderate levels of grief per screening with the Marwit-Meuser Caregiver Grief Inventory-Short Form (scores 25 or above), and/or experiencing high levels of depressive symptoms per screening with PHQ9 (scores 10 or above)
- Caregivers whose care recipients die during the course of the intervention will remain in the study

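### The adverse event definition in section 7.3 conflicts with its CES-D example for caregivers already above 16 at baseline, so the AE count may be dominated by pre-existing symptoms and cannot by itself show worsening

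*Combined protocol and SAP*

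**What the plan says.** Section 7.3 opens with a general definition: an unfavorable finding is an AE when it occurs during the study, "having been absent at baseline, or if present at baseline, appears to worsen". The same paragraph then offers an example expected in this trial, namely a "Center for Epidemiological Studies-Depression Scale (CES-D) score greater than 16 points, indicative of risk for clinical depression" obtained during data collection. It closes by saying that, whether or not the "score is associated with study participation, we will monitor and report it as an AE, per protocol".

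Section 7.1 sets the same absolute cut-off as a safety parameter. Section 7.2 says the parameters "will be assessed at: pre-enrollment screening, and the three data collection points (baseline and 8 and 24-weeks". Section 7.5 attaches referral and follow-up to participants who experience AEs.

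Section 4.1 admits caregivers with moderate to high grief "and/or experiencing high levels of depressive symptoms per screening with PHQ9 (scores 10 or above".

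Section 9.1 describes the CES-D as a 0 to 60 scale with test-retest reliability of .45 to .70. Section 6.1 schedules depressive symptoms at baseline, 8 weeks and 24 weeks.

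**The concern.** The general definition compares a finding with the participant's own baseline. The example uses a fixed cut-off with no such comparison. A score taken at baseline can be neither absent at baseline nor worse than baseline, so it can never meet the definition, yet the example read literally reports it. The same problem arises at follow-up for a caregiver who was above 16 at entry and has not changed. Two coders working from section 7.3 could record the same caregiver differently.

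This matters here because entry selects for distress, so a sizeable share of the sample may exceed 16 before any session takes place. A caregiver who stays at 20 and one who goes from 20 to 45 would then produce the same AE record. Section 7 expects emotional upset mainly in the last four sessions, so whoever reads the AE tally needs to be able to tell new or worsening symptoms from those brought into the trial.

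**Working it through.** The documents state no AE count or rate, so there is no planned figure to reproduce. The check has two parts: how each rule classifies the possible cases, and how many flags could be affected.

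**Classification of a CES-D score above 16**

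| Case | Cut-off example, read literally | General definition |
|---|---|---|
| Baseline score itself | AE | Not an AE |
| Follow-up, above 16 at baseline, no rise | AE | Not an AE |
| Follow-up, above 16 at baseline, higher score | AE | AE, if the rise counts as worsening |
| Follow-up, 16 or below at baseline | AE | AE |

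The rules disagree in the first two rows. The third depends on how much rise counts as worsening, which the protocol does not say.

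**Inputs**

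- N = 144 (section 9.2). Full follow-up is assumed for simplicity, although 10% attrition is planned.
- Three CES-D visits (section 6.1).
- Correlation r between baseline and each follow-up score: 0.45 to 0.70, taking the test-retest range in section 9.1.
- Share p above 16 at baseline: not given. The working value of 40% borrows the section 2.1 figure of up to 40% depression among dementia caregivers generally. That is not a CES-D figure for this sample, so p is varied from 20% to 80%.
- Model assumption: baseline and follow-up scores are bivariate normal, with the same p at each visit and no treatment effect.

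**Flags under the literal rule**

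- Baseline: 144 × 0.40 = 57.6, about 58.
- All three visits: 3 × 57.6 = 172.8, about 173.

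**How many fail the definition**

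Let q be the probability of being above 16 at a follow-up given above 16 at baseline. For p = 40% the model gives q = 0.576 at r = 0.45 and 0.694 at r = 0.70.

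- Follow-up flags in caregivers above 16 at baseline: 2 × 57.6 × q = 66 to 80.
- New-onset flags at follow-up: 2 × 57.6 × (1 − q) = 49 down to 35.

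Among caregivers above 16 on both occasions, half have risen and half have not, by symmetry. If any rise counts as worsening, the failing flags are all baseline flags plus half of the 66 to 80:

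- Share failing, all three visits = (p + 2p × q/2) / 3p = (1 + q)/3. For p = 40%: 1.576/3 = 0.53 to 1.694/3 = 0.56.
- Share failing, follow-up visits only = q/2. For p = 40%: 0.29 to 0.35.

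**Range for p = 20% to 80%** (q from 0.41 to 0.89)

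| Flags counted | Any rise counts as worsening | Rise of at least 0.5 SD needed |
|---|---|---|
| All three visits | 47% to 63% fail | 55% to 79% fail |
| Follow-up only | 20% to 45% fail | 32% to 68% fail |

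The any-rise column follows from the formulas above. The 0.5 SD column comes from simulating the same model with 2,000,000 draws; at p = 40% with all visits counted it gives 63% to 70%.

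**The case against.** Section 7.3 calls the high score an example, directly after the general definition, so it can be read as subject to that definition. The phrase about association concerns relatedness to study participation, not baseline status. Section 7.2 says when parameters are assessed, not that every assessment creates an AE, and no section says that an unchanged score becomes a new event at each visit. Section 7.4 also refers to a Data Safety Monitoring Plan that is not among the documents and may hold recording rules. All of this stands. It makes the literal reading one of two, but it does not remove the conflict, because the text attaches no baseline condition to the example.

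A reader might infer that the AE table will certainly consist mostly of baseline depression. The documents do not support that. The baseline share above 16 is unknown, and grief alone can qualify a caregiver under section 4.1. With follow-up visits only and any rise counted as worsening, fewer than half of the flags fail. It would also be wrong to picture a handful of true events among a mass of stable ones: ordinary fluctuation in scores alone would produce 35 to 49 new-onset flags at 40% prevalence.

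A reader might also infer that real deterioration would be hidden, or that a between-arm AE comparison would be diluted. Neither follows. The CES-D is a secondary outcome modelled by arm (sections 9.4 and 9.5), the Safety Officer reviews data as well as adverse events (section 7.6), and suicidal ideation is reported separately as an SAE (section 7.3). Section 9.5 plans no between-arm comparison of AEs. The limitation belongs to the AE tally. It is not wholly idle, because section 9.3 plans no interim analysis and the monitored items named in section 10.3.4 include adverse events but not change in CES-D.

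**Conclusion.** The conflict within section 7.3 is real and rests on the text alone. Followed literally, the CES-D rule records AEs that fail the protocol's own definition, and the resulting count cannot separate a stable score from a worsening one.

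The size is conditional. At an assumed 40% baseline prevalence and with all three visits counted, slightly more than half of about 173 flags would fail. That proportion depends on the unstated prevalence, on whether baseline scores are counted, on the undefined meaning of worsening, and on a model with full follow-up and no treatment effect. The supportable statement is that AE counts may be dominated by pre-existing symptoms, not that they will be. No efficacy estimate is affected, including the CES-D secondary-outcome analysis.

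**What to change.** Reconcile sections 7.1, 7.2, 7.3 and 7.5 so that they state how three things are recorded: a score already above 16 at baseline, a repeat score above 16, and worsening. Section 7.5 has to be included because referral there depends on having an AE, so rewording the AE rule on its own could alter who is referred.

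In the safety summaries for the Safety Officer and in the final report, tabulate CES-D flags by arm in three rows:

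- (a) above 16 at baseline;
- (b) newly above 16 after baseline;
- (c) above 16 at baseline with a later rise.

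Pre-specify the rise that counts in row (c), since counting any rise is sensitive to test-retest noise. Base any between-arm safety comparison on rows (b) and (c).

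This changes tabulation only. The score threshold, referral and participant management remain for the sponsor to settle. The scores are already scheduled at all three visits, so the cost is a wording change and slightly longer AE tables.
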